 - a. Participants will be screened to be fluent in English, between the ages of 18-30, and to have no contraindications for TMS. Participants will also be screened such that they do not belong to populations vulnerable to the Coronavirus Disease (COVID-19) and have not been exposed. They will also be asked to indicate whether they have received

PROTOCOL TITLE: TMS Studies of Working Memory and Cognitive Control

a full FDA-authorized COVID-19 vaccination series, the specific vaccine product they received, and the date of complete vaccination.

- Demographics
 - a. Demographic information including age, gender, race, and ethnicity will be collected. This information will be used for reporting purposes to demonstrate fair inclusion. Participants will be informed that providing this information will be optional. This information has no direct bearing upon the research to be performed
- Follow-up Form
 - a. One month after the last TMS session, participants will be contacted and asked to fill out a follow-up form. This form inquires about possible experiences the participant may have had that may be attributable to TMS. This information will be used to assess any possible risks of TMS.

6.3 *Describe:*

- *Procedures performed to lessen the probability or magnitude of risks.*
- *All drugs and devices used in the research and the purpose of their use, and their regulatory approval status.*
- *The source records that will be used to collect data about subjects. (Attach all surveys, scripts, and data collection forms.)*

To lessen the probability or magnitude of risks, researchers will stop testing or administer breaks if participants feel frustrated, tired, and/or uncomfortable. Additionally, the occurrence of any adverse events associated with this study and its procedures, as well as any changes in risk level, will be monitored by the principal investigator and co-investigators.

The most severe risk is that of seizure. The risk of seizure will be minimized in two ways 1) Using stimulation parameters that are within the safety guidelines reported by Rossi et al., 2009, and 2) Excluding participants at increased risk for seizure as indicated in the exclusion criteria. Within the stimulation parameters to be used in the present protocol, no seizures have been reported resulting from TMS in the populations that we

PROTOCOL TITLE: TMS Studies of Working Memory and Cognitive Control

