9.0 Study Timelines*

9.1 Describe:

- *The duration of an individual subject's participation in the study.*
- *The duration anticipated to enroll all study subjects.*
- *The estimated date for the investigators to complete this study (complete primary analyses)*

The duration for each individual's participation will be between 1 and 2 hours per session. Participants will participate in at least 1, and potentially several sessions. It may take up to several weeks to complete an entire task. The duration anticipated to enroll all study subjects is 72 months.

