
Local pain, headache, or discomfort. The most commonly reported side effect of TMS is headache. This headache is typically of a muscle-tension type. It usually develops during or immediately after the stimulation and may last for minutes to hours following the end of the stimulation. It is typically limited to the day of stimulation. Neck pain or scalp pain may also occur. Both are usually managed easily with over-the-counter analgesics. The experimental procedure will be immediately terminated whenever anyone reports

PROTOCOL TITLE: TMS Studies of Working Memory and Cognitive Control

experiencing discomfort. There are no reports of any such effects recurring. For many scalp locations, TMS feels only like a sudden tap on the scalp accompanied by a clicking sound. For other scalp locations, TMS can cause face or limb twitches. These twitches are not painful, but can feel odd or disquieting when first experienced. On some occasions, TMS might cross the threshold to the point where it would actually be described as producing a slightly painful scalp sensation. We will closely monitor subjects' comfort and will request them to tell us if the stimulation ever feels painful. If this occurs, we will immediately decrease TMS intensity to a level that is not painful. It is important to note that the likelihood of headache and other discomfort depends upon the stimulation parameters.

Parameters for clinical applications for depression note a rate of 28% for pain, which is greater than the 16% observed for sham (i.e. no true stimulation; Loo et al., 2008). However, for TBS, the rate is less than 3% (Oberman et al., 2011). In many cases, discomfort can be due to neck pain resulting from holding one's head still against the coil. The figure 8 coil (MCF-B65) is lightweight compared to most coils and will be supported by an arm for positioning that alleviates downward pressure on the subject. Therefore, we anticipate rates of adverse effects due to pain and discomfort will be low and in accordance with the PI's previous history with the technique.

Transient hearing changes. TMS produces an audible clicking noise when the current passes through the coil. This click can result in tinnitus and transient decreased hearing if no protection is used. To prevent this adverse effect, all experimental participants will wear ear plugs. Animal and human studies have demonstrated that earplugs can effectively prevent the risk of hearing disturbances or discomfort due to TMS.

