18.0 Provisions to Monitor the Data to Ensure the Safety of Subjects*

This section is required when research involves more than Minimal Risk to subjects.

18.1 *Describe:*

- *The plan to periodically evaluate the data collected regarding both harms and benefits to determine whether subjects remain safe. The plan might include establishing a data monitoring committee and a plan for reporting data monitoring committee findings to the IRB and the sponsor.*
- *What data are reviewed, including safety data, untoward events, and efficacy data.*

- *How the safety information will be collected (e.g., with case report forms, at study visits, by telephone calls with participants).*
- *The frequency of data collection, including when safety data collection starts.*
- *Who will review the data.*
- *The frequency or periodicity of review of cumulative data.*
- *The statistical tests for analyzing the safety data to determine whether harm is occurring.*
- *Any conditions that trigger an immediate suspension of the research.*

The primary safety risk of TMS is seizure. Any seizures resulting from TMS will be reported to the IRB. The incidences of seizures will be monitored. If it appears that the incidences of seizures observed in the study are statistically higher than those reported in the literature (e.g. through the use of a chi-square test), the IRB will be alerted and the safety protocol will be revisited.

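### The only side-effect form described comes one month after the last TMS session, so short-lived effects are at risk of under-recording

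*Combined protocol and SAP*

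**What the plan says.** Section 6.2 describes a single form on side effects. Its timing is "One month after the last TMS session, participants will be contacted and asked to fill out a follow-up form", its content is "This form inquires about possible experiences the participant may have had that may be attributable to TMS", and its purpose is "This information will be used to assess any possible risks of TMS". No item list, recall window or grading is given.

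Section 15.1 states that "The most commonly reported side effect of TMS is headache". It places the onset during or just after stimulation and the duration at minutes to hours, and adds that "It is typically limited to the day of stimulation". It predicts that "we anticipate rates of adverse effects due to pain and discomfort will be low".

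Section 9.1 allows one or more sessions per person and says "It may take up to several weeks to complete an entire task".

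Symptoms are also asked about by word of mouth: during motor-threshold finding (6.1), periodically during the procedure (6.3), and, for light-headedness or dizziness, straight after stimulation (15.1). Section 6.3 says the principal investigator and co-investigators will monitor adverse events in general. Section 15.1 has syncope reported to the IRB.

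On cumulative review, 18.1 says "The incidences of seizures will be monitored" and names no other event. Section 4.2 gives safety endpoints as not applicable.

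**The concern.** The form exists to assess the risks of TMS, but it is given long after the effect that the protocol ranks first will have passed. A participant must recall a headache of a few hours from a month earlier, or from longer ago if it followed the first of several sessions. The verbal queries fall at a better time, but the plan does not say that their answers become data.

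At stake is whether the study can count the minor effects it is most likely to see, and so whether its own forecast of low rates of pain and discomfort can be checked. Section 18.1 asks which safety data are reviewed, how they are collected and how often; the answer covers only seizure, the rarest of the events that the protocol discusses.

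**Working it through.** The plan gives no figure to reproduce: there is no safety endpoint and no target precision for a side-effect rate. The check has three parts.

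**1. Timing and recording, side by side**

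| Moment | What is asked | Section | Recording stated? |
|---|---|---|---|
| Motor-threshold finding | Discomfort or unusual symptoms | 6.1 | No |
| During the procedure | Discomfort | 6.3 | No |
| Straight after stimulation | Light-headedness, dizziness | 15.1 | No |
| End of session (optional) | Task strategy only | 6.2 | Not a symptom question |
| After leaving, before any later session | Nothing described | – | – |
| Before stimulation at a later session | Nothing described about after-effects | – | – |
| One month after the last session | Experiences possibly due to TMS | 6.2 | Yes, a form |

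The delay from effect to form is one month for a single session. For the first of several sessions it is one month plus the time between first and last session, which 9.1 allows to reach several weeks. The effect itself lasts minutes to hours. The repeat screening form in 10.1 belongs to entry screening. Section 6.4 lists identifiers, brain activity, and task accuracy and speed as the data collected, with no symptom data.

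**2. What incomplete capture would do (illustration)**

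Inputs: N = 400 (12.1); true rate p = 3%, which 15.1 cites as an upper bound for theta-burst stimulation; capture fraction c, which the documents do not give and which is assumed here over a range. One report per person is counted. Expected recorded cases = N × p × c; apparent rate = p × c. Intervals are exact (Clopper-Pearson) 95%, at the nearest whole count.

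| c (assumed) | Expected cases | Apparent rate | 95% CI |
|---|---|---|---|
| 100% | 400 × 0.03 = 12 | 3% | 1.6% to 5.2% |
| 90% | 10.8 | 2.7% | 1.4% to 4.9% |
| 75% | 9 | 2.25% | 1.0% to 4.2% |
| 50% | 6 | 1.5% | 0.6% to 3.2% |
| 25% | 3 | 0.75% | 0.15% to 2.2% |

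Only at 25% capture does the interval exclude the true 3%. At higher rates the loss would show sooner. With the 28% pain rate that 15.1 cites for clinical depression treatment, 400 × 0.28 = 112 cases are expected; capture of 75% gives 84 (21%, CI 17.1% to 25.3%) and 50% gives 56 (14%, CI 10.8% to 17.8%), and both intervals exclude 28%. Section 6.1 says the study's parameters differ from clinical ones, so this is an outer case and not a forecast.

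**3. What 18.1 follows instead**

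Section 15.1 cites 16 seizures among tens of thousands of people. Taking 10,000 as the smallest denominator that fits (an assumption), 400 × 16 / 10,000 = 0.64 expected seizures; any larger denominator gives fewer. The named review therefore follows an event expected less than once, while up to 12 participants could have pain or discomfort at the cited theta-burst bound.

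**The case against.** The strongest reply is that the protocol does ask at the right time. Headache usually starts in the window that the in-session queries cover, participants are encouraged to report discomfort, and reported discomfort leads to action by staff, so in-session reactions should become known. Section 6.3 commits the investigators to monitoring adverse events, and the one-month form has a stated use. The study's aim is cognitive, with no safety endpoint and no stated plan to publish a side-effect rate. Forms and appendices are said to be attached but are not in the text available, so a session form may exist.

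Much of this stands, and it rules out several stronger readings that a reader might infer:

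- That rates *will* be under-recorded. With full capture at the session there would be no bias, and the documents do not say what capture will be.
- That a participant who reacted could be stimulated again without ever having been asked. Staff ask during stimulation and, about dizziness, straight afterwards. What is not described is a question about after-effects before the next stimulation.
- That the form feeds no review. Sections 6.2 and 6.3 give it a purpose and provide general monitoring; the gap is that 18.1 does not mention it.
- That the study would report 1.5% in place of 3%. That needs an assumed 50% capture with the one-month form as the only route, and 6 of 400 is still compatible with 3%.

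The reply does not supply a record. No section says that the verbal answers are written down, graded or counted. The one query placed explicitly after stimulation covers light-headedness and dizziness, not headache, neck pain or hearing change. Nothing covers the hours after the participant leaves.

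**Conclusion.** The concern holds as a risk of under-recording. The one side-effect form described is badly timed for short-lived effects, the better-timed queries have no stated record, and 18.1 links neither to a cumulative review. Effects that start or persist after the participant leaves are the most exposed.

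The size cannot be fixed from the documents. The range of 0.75% to 2.7% for a true 3% rests on an assumed capture of 25% to 90%, on an upper bound cited for theta-burst stimulation only (the study also uses 1 Hz and online stimulation), and on one report per person. The conclusion also assumes that no session form sits in the attachments. With no safety endpoint in the study, this is a worthwhile improvement and not a flaw that threatens the main results.

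**What to change.** - **6.2:** complete the existing form at the end of each session, recording the answers to the verbal queries already planned. Complete it again at the start of each later session, before stimulation, asking about the time since the last session.
- **6.2:** keep the one-month form for late effects. It would remain the only capture of effects that start after a participant's last or only session, and the protocol should say so.
- **6.4:** list the symptom data among the data collected.
- **18.1:** add the counts of headache, pain, dizziness or syncope, and hearing change to the review, beside seizures.
- If a session form already exists in the attachments, name it in 6.2 and 18.1.

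The change is cheap: probably a few minutes per session (the form itself was not available to time) and a few more rows in the review. The downside is that recorded rates of minor effects will look higher. No stimulation setting or management rule changes.

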9.0 Study Timelines*

9.1 Describe:

- *The duration of an individual subject's participation in the study.*
- *The duration anticipated to enroll all study subjects.*
- *The estimated date for the investigators to complete this study (complete primary analyses)*

The duration for each individual's participation will be between 1 and 2 hours per session. Participants will participate in at least 1, and potentially several sessions. It may take up to several weeks to complete an entire task. The duration anticipated to enroll all study subjects is 72 months.

10.0 Inclusion and Exclusion Criteria*

10.1 Describe how individuals will be screened for eligibility.

Participants will be screened in order to minimize risks associated with TMS. Screening will proceed in two phases. First, the screening form will be sent to the participant via e-mail (see Appendix). The participant will be asked to respond with whether the answer to any question on the screening form is “yes.” At this phase, the participant does not need to indicate to which question the answer is “yes.” If the response is “yes” to any question, the participant will be excluded. If the participant passes the first phase of screening and remains interested in participating, the participant will be invited to perform the study. Participants will read the consent form and any questions will be answered. After answering questions, the participant will once again be presented with the screening form. In this case, the participant will fill-out the screening form. If the answer is “yes” to a given question, the participant may be asked to elaborate. A “yes” response may occur in the second screening, but not the first, if circumstances changed since the initial screening. The individuals included in this study will be adults from ages 18 to 30.

We will also exclude from study individuals who are vulnerable to or may have come in contact with COVID-19. We will include individuals who have completed a full FDA-authorized vaccination series at least 14 days before the study session, and individuals who have not been fully vaccinated provided that they pass the screening process. As with the other screening forms, the COVID-19 screening

PROTOCOL TITLE: TMS Studies of Working Memory and Cognitive Control

form will be sent to the participant via e-mail (see Appendix). The participant will be asked to respond with whether the answer to question #1 on the form is “yes” or if, alternatively the answer to #1 is “no” and the answer to any other question on the screening form (#2 through #8) is “yes.” Question #1 asks participants to indicate if they have received a complete vaccination series, the specific FDA-approved vaccine product they received, and the date of vaccination. At this phase, the participant does not need to indicate which to which of the other questions the answer is “yes.” If the response is “yes” to any questions including #2 through #8, the participant will be excluded. If the participant passes the first phase of screening and remains interested in participating, the participant will be invited to perform the study. Participants will read the consent form and any questions will be answered. After answering questions, the participant will once again be presented with the screening form. In this case, the participant will fill-out the screening form. If the answer is “no” to #1 and “yes” to any of the other questions (#2 through #8), the participant may be asked to elaborate. A “yes” response may occur in the second screening, but not the first, if circumstances changed since the initial screening.

10.2 Describe the criteria that define who will be included or excluded in your final study sample.

Inclusion: Because we are interested in the mental function of adults prior to any age-related decline, participants will be between the ages of 18-30. Participants will also need to be fluent in English and have acquired fluency prior to the age of 6 since English is required to understand the instructions and some tasks will use English words/letters as stimuli.

Exclusion: Left-handed people will be excluded. Many brain functions are lateralized (e.g. language is often processed by the left hemisphere).

Based on recommendations of the International Workshop on the Safety of Repetitive Transcranial Magnetic Stimulation (reported in Wassermann, 1998), as well as the recommendations of Rossi et al., 2009, we will exclude subjects on any of the following grounds: Metal anywhere in the head, excluding the mouth, History of seizures, Family history of epilepsy, Vascular, traumatic, tumoral, infectious, or metabolic lesion of the brain, Stroke, Chronic, or transient insomnia (e.g. jet lag), Alcoholism, Severe headaches, Cardiac pacemakers, Current use of medication for neurological or psychiatric conditions, Tinnitus, and Pregnancy. While the health risks to the fetus are unknown, magnetic field strength decreases approximately with the cube-root of the distance from the magnetic

PROTOCOL TITLE: TMS Studies of Working Memory and Cognitive Control

coil. Therefore, a coil located on the scalp will have little direct effect on the abdomen, though changes in neural firing or emotional stress levels could in theory have distal impact. Nevertheless, any person who is pregnant will be excluded from the study. Additionally, people with the following will be excluded: hearing impairments and permanent retainers on the top portion of their jaw. A screening form (attached) will be used to assess each subject's eligibility for participation.

10.3 Indicate specifically whether you will include or exclude each of the following special populations: (You may not include members of the above populations as subjects in your research unless you indicate this in your inclusion criteria.)

- *Adults unable to consent*
- *Individuals who are not yet adults (infants, children, teenagers)*
- *Pregnant women*
- *Prisoners*

Special populations will not be studied.

11.0 Vulnerable Populations*

11.1 If the research involves individuals who are vulnerable to coercion or undue influence, describe additional safeguards included to protect their rights and welfare.

NA

12.0 Local Number of Subjects

12.1 Indicate the total number of subjects to be accrued locally.

The total number of subjects to be accrued locally is 400.

12.2 If applicable, distinguish between the number of subjects who are expected to be enrolled and screened, and the number of subjects needed to complete the research procedures (i.e., numbers of subjects excluding screen failures.)

NA

13.0 Recruitment Methods

13.1 Describe when, where, and how potential subjects will be recruited.

Recruitment will be conducted at Florida State University at least one hour before testing. Potential subjects will be recruited via voluntary responses to flyers posted around campus and responses to approved electronic postings (see Appendix). Flyers will also be posted around local areas (e.g. coffee shops, restaurants).

Additionally, flyers will be given to participants who have

PROTOCOL TITLE: TMS Studies of Working Memory and Cognitive Control

volunteered for similar studies. (A paper flyer will be given to participants who have volunteered for similar studies after they have completed the study. These participants will have completed a study in a lab at Florida State University that uses similar methods to us and has agreed to hand out flyers for our studies to their participants). Volunteers will email or call a trained research technician who will screen the subject by the stated criteria. Potential subjects will be instructed to meet either in the [name] lab in the Psychology Building, [name] lab in the Psychology Building, or the MRI facility at the College of Medicine. All of these are private and secure locations requiring key card access.

13.2 Describe the source of subjects.

The source of subjects will be from Florida State University or the local community as long as subjects are eligible based on inclusion and exclusion criteria.

13.3 Describe the methods that will be used to identify potential subjects.

The methods used to identify potential subjects include the inclusion criteria and “no” responses to TMS screening questions.

13.4 Describe materials that will be used to recruit subjects. (Attach copies of these documents with the application. For advertisements, attach the final copy of printed advertisements. When advertisements are taped for broadcast, attach the final audio/video tape. You may submit the wording of the advertisement prior to taping to preclude re-taping because of inappropriate wording, provided the IRB reviews the final audio/video tape.)

Materials to recruit subjects include an online advertisement and recruitment advertisements posted throughout Florida State University. These documents are attached, along with a sample recruitment email response from a researcher.

13.5 Describe the amount and timing of any payments to subjects.

Participants will receive \$15 per hour or credit hours associated with the undergraduate Psychology course. Paid participants may also receive a performance-based bonus as incentive to perform the task to the best of their ability. Such incentives will only be available to paid participants and will be based upon accuracy and speed on the tasks and will tend to total \$0-\$5 per hour. In the event of a multisession study, paid participants may also receive a completion bonus. Participants that withdraw from the study prior to completion will receive prorated compensation (either monetary or credit hours) commensurate with the duration of participation. Lastly, monetary compensation or credit hours will be awarded once the study is complete, or after the subject withdraws from the study.

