6.0 Procedures Involved*

6.1 Describe and explain the study design.

In the proposed research, we will use computer-based tasks that engage cognitive control and/or working memory. Typical paradigms will involve presenting stimuli such as words, letters, pictures, or sounds. In tasks involving working memory, participants will be asked to retain in mind some aspect of the stimulus after it is no longer present on the monitor. In tasks involving working memory and/or cognitive control, participants will make decisions on stimuli that are based on previous instruction and previous stimuli. Since cognitive control interacts with the reward system (i.e. to motivate cognitive control), we will also examine reward-related tasks either in tandem with cognitive control, or in isolation.

TMS will be delivered in one of two modes: 1) In "online" studies, TMS will be time-locked to the task (for example, a single pulse may be delivered 20, 60, or 100 ms after the onset of the stimulus) and we will investigate the critical period of involvement of a given region. Such studies will involve either single pulses of TMS or short burst

PROTOCOL TITLE: TMS Studies of Working Memory and Cognitive Control

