
PROTOCOL TITLE: TMS Studies of Working Memory and Cognitive Control

following TMS, or both. The EEG assesses electrical brain activity through surface recording disks (electrodes) which are placed near the participant's head. The electrodes transmit the signals, which are then amplified (via an 8 channel Brain Vision LiveAmp) and stored on a computer. The procedure is entirely non-invasive.

An electrode cap will be placed on the participant's head. In order to record brain activity, these disks need to be filled with a gel which allows the electrodes to better record brain activity at the scalp.

Therefore, the participants in this study will need to clean their hair after participation. The gel is completely water soluble, and the procedure is painless. The MRI facility has sinks and towels, and the investigators will help to make sure the participant has thoroughly rinsed all the gel from their hair. After an accurate signal is assured, the signal derived from the electrode cap is then amplified, transmitted to a computer, and stored for later analysis.

In addition to the EEG recording, muscle activity from around the eyes may be recorded from the subjects. Muscle activity from around the eyes is recorded by two small sensors that will be placed below the participant's left eye, as well as behind the ears. These procedures are completely noninvasive and painless.

6.2 *Provide a description of all research procedures being performed and when they are performed, including procedures being performed to monitor subjects for safety or minimize risks.*

Below is a description of the kinds of tasks that participants may perform in a piecemeal fashion. It is likely that elements from multiple such tasks will be combined into a single task. Hereafter, stimuli will refer to letters, numbers, words, pictures, or sounds. Unless otherwise specified, stimuli will be affectively neutral. In general, tasks will range in duration from 5-10 minutes to 1-2 hours. Breaks will be given every 5-10 minutes. Multiple sessions may be performed. Based upon performance on the tasks, we may contact participants to perform other related tasks. Returning to perform other tasks will be optional and have no bearing upon the tasks the participants have already completed.

- Computer-based Tasks
 - Short-term memory

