 - a. In this task, participants are presented with a set of stimuli to remember. After a delay, participants will receive a test item. The test item can either be an old/new stimulus requiring a recognition decision (i.e. was the stimulus a member of the set?) or it can be a stimulus to be transformed to match a

PROTOCOL TITLE: TMS Studies of Working Memory and Cognitive Control

stimulus in the set (e.g. rotate a grating until it matches a grating in memory).

- Span
 - a. In this task, participants will be presented with a list of stimuli to remember. In some cases, they will be asked to make judgments in-between the presentation of memoranda (e.g. assess the validity of a simple arithmetic expression). Upon termination of the list, participants will be asked to reproduce the list.
- Change-detection
 - a. In this task, participants will see a collection of stimuli, followed by another collection of stimuli. They will respond with whether the collection changed or not.
- Sequence Memory
 - a. In this task, participants will learn a predefined stimulus sequence. Participants will make judgements regarding whether the presented stimuli follow the predefined sequence or not.
- Alternative forced choice
 - a. In this task, participants will judge the categorical status of stimuli. Categories include word/non-word judgements, semantic judgements, number judgements (e.g. is the number odd or even), object category judgments (e.g. face, scene), and spatial judgments (e.g. which direction does an arrow point).
- Cued attention
 - a. In this task, participants will be directed to attend to a particular stimuli, regions of space, or location of sound. Participants will make either alternative forced choice or memory judgements regarding the attended stimuli.
- Task-switching

PROTOCOL TITLE: TMS Studies of Working Memory and Cognitive Control

- a. In this task, participants will switch among two or more tasks of the nature described above.
- Doors Task
 - a. Participants will be shown graphics depicting doors, and will be asked to choose a door. After picking a door, participants receive feedback on the screen indicating whether they have won or lost on that trial. The participants' goal is to do their best to win as much money as possible. In this task, participants will receive a monetary bonus for correct guesses, which will total between \$0.00 and \$10.00 depending on how many correct guesses they make. This task will take approximately 5-10 minutes.

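### Do sections 6.2 and 13.5 leave course-credit participants playing the Doors Task for no real money?

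*Combined protocol and SAP*

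**What the plan says.** Section 6.2 describes the Doors Task. Participants choose among pictured doors, see whether they won or lost, and are to "do their best to win as much money as possible". On payment it says: "In this task, participants will receive a monetary bonus for correct guesses", with a total between $0.00 and $10.00 set by the number of correct guesses. On length it says: "This task will take approximately 5-10 minutes". Nothing there separates paid from credit participants. The same section introduces its task list as the "kinds of tasks that participants may perform in a piecemeal fashion", so Doors is one option among many.

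Section 13.5 answers the template prompt "Describe the amount and timing of any payments to subjects". Compensation is $15 per hour or "credit hours associated with the undergraduate Psychology course". Paid participants may also earn a performance bonus: "Such incentives will only be available to paid participants and will be based upon accuracy and speed on the tasks". The usual total is given as $0-$5 per hour. The only other bonus named is one for paid participants who complete a multisession study. The Doors bonus does not appear.

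Section 6.1 makes reward part of the research: "we will also examine reward-related tasks either in tandem with cognitive control, or in isolation".

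**The concern.** In the Doors Task money is the experimental stimulus, not only a thank-you. If the paid-only rule in 13.5 covers the Doors bonus, a credit participant given the task would be told to win money and shown wins and losses, yet collect nothing. Two incentive conditions would then sit under one task name, split by how people chose to be compensated, and section 17.1 says nothing about compensation type. Data already collected without stakes could not later be turned into data with stakes.

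If the rule does not cover the Doors bonus, the stakes are real for everyone who plays, but 13.5 has left out a payment that its prompt asked for.

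One version threatens the meaning of the reward data. The other is an incomplete payment section.

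**Working it through.** The plan gives no sample-size or power figure that bears on this point, so there is none to reproduce. The check compares the two sections and adds some simple arithmetic.

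**Inputs.** Doors bonus $0.00-$10.00 and task length 5-10 minutes (6.2). Base pay $15 per hour and performance bonus usually $0-$5 per hour (13.5). Sessions of 1 to 2 hours (9.1). 400 participants (12.1).

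**Size of the bonus.**
- Base pay for the task time: 15 × 5/60 = $1.25 and 15 × 10/60 = $2.50.
- Maximum Doors bonus relative to that pay: 10/2.50 = 4 and 10/1.25 = 8.
- Usual upper end of the 13.5 bonus per session: 5 × 1 = $5 and 5 × 2 = $10. The Doors maximum equals the 2-hour figure and exceeds the 1-hour figure by $5. Section 13.5 describes a tendency, not a cap, so this is not a contradiction.
- Upper limit on cost if everyone were on credit, played once and won the maximum: 400 × 10 = $4,000.

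The ratio of 4 to 8 shows that the stake is not trivial to the player. It does not measure any difference between paid and credit participants.

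**Readings, tested against both sections.**

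| Reading | 6.2 (all who play are paid for correct guesses) | 13.5 (performance bonus for paid participants only) | Effect on data |
|---|---|---|---|
| A. Doors is given only to paid participants | holds | holds | none |
| B. The Doors bonus is separate from the 13.5 incentives | holds | holds, but the list of payments is incomplete | none |
| C. Credit participants play and receive nothing | breached | holds | mixed stakes |

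A is open because the tasks are a menu and no section assigns credit participants to Doors. B is supported by the wording: 13.5 ties its incentives to how accurate and fast people are and makes them optional, whereas the Doors bonus depends on correct guesses, has no stated speed element and is promised. C is the only reading with a consequence for the data, and it requires staff to depart from 6.2.

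**What C would do to a TMS comparison.** Section 6.1 says the critical analyses compare accuracy and speed across TMS settings, not across compensation types. Let δ be the TMS effect, m the difference in mean outcome between credit and paid participants, and p₁ and p₀ the shares of credit participants in the two TMS conditions compared. With δ the same in both groups, the expected contrast is

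δ + m(p₁ − p₀).

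The added term is zero when the shares are equal, and they are necessarily equal when each person serves in both conditions. If δ differs by compensation type and the shares are equal, the contrast is a weighted average of the two effects. That would blur what is being estimated. The documents give no value for m, p₁ or p₀, so no bias can be put in figures.

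**The case for a change.** The strongest case for a change is that 6.2 is mandatory and unrestricted, 13.5 is restrictive, and no section says which prevails for a credit participant. Nothing states that such participants are kept away from Doors, play for points, or are paid as an exception. The text alone therefore does not rule out a laboratory that applies 13.5 to every bonus. Since reward is an object of study and one sentence would settle the matter, it seems sensible to settle it before any reward data are collected.

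Part of this stands. The two sections do not refer to each other, and 13.5 does not list a payment that 6.2 promises. The step to a scientific defect does not. It needs Doors to be used in a particular study, credit participants to be enrolled in that study, those participants to go unpaid despite 6.2, and their data to be pooled with paid participants' data. None of these is stated, and the third contradicts the text. The Motivated Behavior Task adds nothing, because 6.2 does not say that its reward is cash. The consent form and recruitment materials are attached to the application but are not in the reviewed text, and they may already state the terms.

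**Conclusion.** No change to the design or analysis follows. Carried out as 6.2 describes it, the Doors Task offers the same $0-$10 stake to everyone who does it, and two natural readings make 6.2 and 13.5 compatible. What remains is a clerical omission: 13.5 does not list the Doors bonus or say whether credit participants may do the task. Staff running the task can fill that gap by following 6.2, and a cross-reference could be added at any routine revision without affecting a result. The size is at most $10 per participant per run, with no effect on sample size or error rates and no demonstrated bias in a TMS contrast.

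The conclusion assumes that staff pay the Doors bonus to whoever plays, as 6.2 says. If credit participants were in fact run without it, their reward data would have to be kept apart from the paid participants' data. That would be a departure from the protocol, not a flaw in it.
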